7.1.5.3 Post-Treatment Visits

- a. Safety Follow-UP Visit

The mandatory Safety Follow-Up Visit should be conducted approximately 30 days after the last dose of trial treatment (pembrolizumab) or before the initiation of a new anti-cancer treatment, whichever comes first. All AEs that occur prior to the Safety Follow-Up Visit should be recorded. Subjects with an AE of Grade > 1 will be followed until the resolution of the AE to Grade 0-1 or until the beginning of a new anti-neoplastic therapy, whichever

occurs first. SAEs that occur within 90 days of the end of treatment or before initiation of a new anti-cancer treatment should also be followed and recorded. Subjects who are eligible for retreatment with pembrolizumab (as described in Section 7.1.5.5) may have up to two safety follow-up visits, one after the Treatment Period and one after the Second Course Phase.

7.1.5.4 Assessment of Tumor Status (also detailed in 6.1 Study Flow Chart):

- a. During the post-treatment year-1, and post-treatment year-2:
 - i. Clinical evaluation, including physical examination;
 - ii. Hemogram, and biochemistry panels including bilirubin, AST, ALT, ALP, gamma-GT, LDH, albumin, BUN, creatinine, Na, Cl, K, Ca, Mg, P, glucose, TSH, T3, fT4, ACTH and cortisol.
 - iii. CT scan (of neck, chest, and abdomen) and esophagoscopy;
 - iv. Repeated every 3 months.
- b. During the 4th and 5th years after esophagectomy (i.e., the post-treatment year-3, and post-treatment year-4):
 - i. Clinical evaluation, including physical examination;
 - ii. Hemogram, and biochemistry panels including bilirubin, AST, ALT, ALP, gamma-GT, LDH, albumin, BUN, creatinine, Na, Cl, K, Ca, Mg, P, TSH, T3, fT4, TSH, ACTH and cortisol.
 - iii. CT scan (of neck, chest, and abdomen) and esophagoscopy;
 - iv. Repeated every 6 months.

7.1.5.5 Follow-up Visits

Subjects who discontinue trial treatment for a reason other than disease progression will move into the Follow-Up Phase. Every effort should be made to collect information regarding disease status until the start of new anti-neoplastic therapy, disease progression, death, end of the study or if the subject begins retreatment with pembrolizumab as detailed in Section 7.1.5.5. Information regarding post-study anti-neoplastic treatment will be collected if new treatment is initiated.

7.1.5.5.1 Survival Follow-up

Once a subject experiences confirmed disease recurrence or starts a new anti-cancer therapy, the subject moves into the survival follow-up phase and should be contacted by telephone

every 12 weeks to assess for survival status until death, withdrawal of consent, or the end of the study, whichever occurs first.

7.2 Assessing and Recording Adverse Events

An adverse event is defined as any untoward medical occurrence in a patient or clinical investigation subject administered a pharmaceutical product and which does not necessarily have to have a causal relationship with this treatment. An adverse event can therefore be any unfavorable and unintended sign (including an abnormal laboratory finding, for example), symptom, or disease temporally associated with the use of a medicinal product or protocol-specified procedure, whether or not considered related to the medicinal product or protocol-specified procedure. Any worsening (i.e., any clinically significant adverse change in frequency and/or intensity) of a preexisting condition that is temporally associated with the use of the Merck's product, is also an adverse event.

Changes resulting from normal growth and development that do not vary significantly in frequency or severity from expected levels are not to be considered adverse events. Examples of this may include, but are not limited to, teething, typical crying in infants and children and onset of menses or menopause occurring at a physiologically appropriate time.

Merck product includes any pharmaceutical product, biological product, device, diagnostic agent or protocol-specified procedure, whether investigational (including placebo or active comparator medication) or marketed, manufactured by, licensed by, provided by or distributed by Merck for human use.

Adverse events may occur during the course of the use of Merck product in clinical trials, or as prescribed in clinical practice, from overdose (whether accidental or intentional), from abuse and from withdrawal.

All adverse events that occur after the consent form is signed but before treatment allocation/randomization must be reported by the investigator if they cause the subject to be excluded from the trial, or are the result of a protocol-specified intervention, including but not limited to washout or discontinuation of usual therapy, diet, placebo treatment or a procedure.

From the time of treatment allocation/randomization through 30 days following cessation of treatment, all adverse events must be reported by the investigator. Such events will be recorded at each examination on the Adverse Event case report forms/worksheets. The reporting timeframe for adverse events meeting any serious criteria is described in section 7.2.3.1. The investigator will make every attempt to follow all subjects with non-serious adverse events for outcome.

Adverse events will not be collected for subjects during the pre-screening period (for determination of archival tissue status) as long as that subject has not undergone any protocol-specified procedure or intervention. If the subject requires a blood draw, fresh

tumor biopsy etc., the subject is first required to provide consent to the main study and AEs will be captured according to guidelines for standard AE reporting.

7.2.1 Definition of an Overdose for This Protocol and Reporting of Overdose to the Sponsor and to Merck

For purposes of this trial, an overdose of pembrolizumab will be defined as any dose of 1,000 mg or greater (\geq 5 times the indicated dose). No specific information is available on the treatment of overdose of pembrolizumab. Appropriate supportive treatment should be provided if clinically indicated. In the event of overdose, the subject should be observed closely for signs of toxicity. Appropriate supportive treatment should be provided if clinically indicated.

If an adverse event(s) is associated with (“results from”) the overdose of a Merck product, the adverse event(s) is reported as a serious adverse event, even if no other seriousness criteria are met.

If a dose of Merck’s product meeting the protocol definition of overdose is taken without any associated clinical symptoms or abnormal laboratory results, the overdose is reported as a non-serious Event of Clinical Interest (ECI), using the terminology “accidental or intentional overdose without adverse effect.”

All reports of overdose with and without an adverse event must be reported within 24 hours to the Sponsor and within 2 working day hours to Merck Global Safety. (Attn: Worldwide Product Safety; [contact])

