Duration of Participation	
Subjects need to sign the informed consent form to be enrolled into this trial.After a screening phase up to 28 days, each subject will receive adjuvant weekly cisplatin -CRT (cisplatin, 30mg/m²/week x 2; radiotherapy, 180-200 cGy/fraction x 10-13) followed by pembrolizumab (200mg/3 weeks x 18) (approx. a total of 56 weeks).Treatment will continue until the completion of the planned cisplatin-CRT plus 18 cycles of pembrolizumab, or until recurrent disease, unacceptable adverse events, intercurrent illness that prevents further administration of treatment, investigator's decision to withdraw the subject, subject withdrawal of consent, pregnancy of the subject, noncompliance with trial treatment, or administrative reasons requiring cessation of treatment.To detect the tumor recurrence, all patients will be evaluated by pertinent evaluation and imaging studies every 4 cycles of pembrolizumab during treatment phase, then every 3 months for post-treatment year-1 to year-2, and every 6 months for post-treatment year-3 and year-4.Subjects who discontinue for reasons other than recurrent disease will have post-treatment follow-up visits for monitoring disease status as if they were still on treatment until recurrent disease, initiating a non-study cancer treatment, withdrawing consent from study participation, or becoming lost to follow-up.All subjects will be followed (e.g., by telephone or visit) for overall survival until death, withdrawal of consent from study participation, or the end of the study, whichever comes first. After the end of study treatment, each subject will be followed for 30 days for adverse event monitoring. Serious adverse events will be

	collected for 90 days after the end of treatment or for 30 days after the end of treatment if the subject initiates new anticancer therapy, whichever is earlier.
Estimated average length of treatment per patient	56 weeks

[figure not shown]

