5.2.1.2 Dose Modification (Escalation/Titration/Other)

Adverse events (both non-serious and serious) associated with pembrolizumab exposure may represent an immunologic etiology. These adverse events may occur shortly after the first dose or several months after the last dose of treatment. Pembrolizumab must be withheld for drug-related toxicities and severe or life-threatening AEs as per 3 below. See Section 5.6 for supportive care guidelines, including use of corticosteroids.

Table 3.1 Dose Modification Guidelines for Pembrolizumab-Related Adverse Events

Toxicity	Hold Treatment For Grade	Timing for Restarting Treatment	Treatment Discontinuation
Diarrhea/ Colitis	2-3	Toxicity resolves to Grade 0-1	Toxicity does not resolve within 12 weeks of last dose or inability to reduce corticosteroid to 10 mg or less of prednisone or equivalent per day within 12 weeks
	4	Permanently discontinue	Permanently discontinue

Toxicity	Hold Treatment For Grade	Timing for Restarting Treatment	Treatment Discontinuation
AST, ALT, or Increased Bilirubin	2 (AST/ALT : 3-5 x upper limit of normal [ULN]; bilirubin: 1.5-3 x ULN)	Toxicity resolves to Grade 0-1.	Toxicity does not resolve within 12 weeks of last dose or inability to reduce corticosteroid to 10 mg or less of prednisone or equivalent per day within 12 weeks
	3-4	Permanently discontinue	Permanently discontinue
Type 1 diabetes mellitus (if new onset) or Hyperglycemia	T1DM or 3-4	Hold pembrolizumab for new onset Type 1 diabetes mellitus or Grade 3-4 hyperglycemia associated with evidence of beta cell failure	Resume pembrolizumab when patients are clinically and metabolically stable
Hypophysitis	2-4	Toxicity resolves to Grade 0-1. Therapy with pembrolizumab can be continued while endocrine replacement therapy is instituted	Toxicity does not resolve within 12 weeks of last dose or inability to reduce corticosteroid to 10 mg or less of prednisone or equivalent per day within 12 weeks
Hyperthyroidism	3	Toxicity resolves to Grade 0-1	Toxicity does not resolve within 12 weeks of last dose or inability to reduce corticosteroid to 10 mg or less of prednisone or equivalent per day within 12 weeks
	4	Permanently discontinue	Permanently discontinue
Hypo-thyroidism		Therapy with pembrolizumab can be continued while thyroid replacement therapy is instituted	Therapy with pembrolizumab can be continued while thyroid replacement therapy is instituted

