6.0 TRIAL FLOW CHART

6.1 Study Flow Chart

Trial Period:	Screening Phase		Adjuvant Cisplatin-CRT		Pembrolizumab				End of Treatment	Post-Treatment		
Treatment Cycle/Title:	Pre-screening (Visit 1)	Main Study Screening (Visit 2)	1	2	To be repeated beyond 4 cycles				Discon	Safety Follow-up	Year-1 & Year-2	Year-3 & Year-4
					1	2	3	4				
Scheduling Window (Days):		-28 to -1	± 3	± 3		± 3	± 3	± 3	At time of Discon	30 days post discon	Every 3 months	Every 6 months
Pre-screening Consent	V											
Informed Consent		V										
Inclusion/Exclusion Criteria	V	V										
Demographics and Medical History		V										
Prior and Concomitant Medication Review		V										
Trial Treatment Administration ^a			V	V	V	V	V	V				
Survival Status ^b			V	V	V	V	V	V	V	V	V	V
Review Adverse Events ^c				V	V	V	V	V	V	V		
Full Physical Examination		V			V				V	V	V	V
Directed Physical Examination			V	V		V	V	V				
Vital Signs and Weight	V	V	V	V	V	V	V	V	V	V	V	V
ECOG Performance Status	V	V	V	V	V	V	V	V	V	V	V	V
Pregnancy Test – Urine or Serum β-HCG		V			V		V		V			
PT/INR and aPTT		V			V		V		V	V		
CBC with Differential		V	V	V	V	V	V	V	V	V	V	V
Comprehensive Serum Chemistry Panel ^d		V	V	V	V	V	V	V	V	V	V	V
Urinalysis		V			V		V		V	V		

Trial Period:	Screening Phase		Adjuvant Cisplatin-CRT		Pembrolizumab				End of Treatment	Post-Treatment		
	Pre-screening (Visit 1)	Main Study Screening (Visit 2)	1	2	To be repeated beyond 4 cycles					Safety Follow-up	Year-1 & Year-2	Year-3 & Year-4
Treatment Cycle/Title:					1	2	3	4				
Scheduling Window (Days):		-28 to -1	± 3	± 3		± 3	± 3	± 3	At time of Discon	30 days post discon	Every 3 months	Every 6 months
T3, FT4 and TSH		V			V		V		V	V	V	V
ACTH, Cortisol		V			V		V		V	V	V	V
Tumor Imaging ^e		V						V			V	V
Archival or Newly Obtained Tissue Collection ^f		V			V (optional)							
Correlative Studies Blood Collection (optional) ^g		V		V	V (every 4 cycles and recurrence)					V (Year-1 and 2: every 3 months until recurrence)		

^aTrial treatment may be administered up to 3 days before or after the scheduled Day 1 of each cycle due to administrative reasons.

^bOnce a subject experiences confirmed disease recurrence or starts a new anti-cancer therapy, the subject moves into the survival follow-up phase and should be contacted by telephone every 12 weeks to assess for survival status until death, withdrawal of consent, or the end of the study, whichever occurs first.

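### General adverse event collection ends 30 days after treatment in most sections but runs into follow-up in 7.1.2.1; under the 30-day rule, first-onset late non-serious immune-related events need not be recorded

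*Combined protocol and SAP*

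**What the plan says.** The general rule is in 7.2: "From the time of treatment allocation/randomization through 30 days following cessation of treatment, all adverse events must be reported by the investigator". The trial summary (1.0) agrees: "After the end of study treatment, each subject will be followed for 30 days for adverse event monitoring". Section 5.8 repeats it, and 7.1.5.3 says of the visit at about day 30: "All AEs that occur prior to the Safety Follow-Up Visit should be recorded". In the 6.1 flow chart the row "Review Adverse Events" is ticked up to the 30-day safety visit and is blank for post-treatment Years 1-2 and 3-4.

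Section 7.1.2.1 reads differently. It has adverse events graded and recorded across the whole study and into follow-up. It also points to the flow chart for assessment times and to 7.2 for recording.

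On late onset, 5.2.1.2 refers to both serious and non-serious events of possible immunologic cause and says: "These adverse events may occur shortly after the first dose or several months after the last dose of treatment". The post-treatment panel in 7.1.5.4 includes "albumin, BUN, creatinine, Na, Cl, K, Ca, Mg, P, glucose, TSH, T3, fT4, ACTH and cortisol". It is done every 3 months in Years 1-2, and the endocrine tests continue every 6 months in Years 3-4, together with physical examination. The definition of an adverse event in 7.2 extends to an "unintended sign (including an abnormal laboratory finding, for example").

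Toxicity and safety are a secondary objective (3.2). Section 8.2.2.3 summarises incidence and severity and states no time window.

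**The concern.** The protocol expects non-serious immune-related events after treatment ends and keeps testing for some of them. Its main recording rule closes before the first of those test visits. A thyroid or adrenal abnormality first found there can be an adverse event by definition, but no rule other than the general sentence in 7.1.2.1 requires it to be recorded, graded or assessed for cause.

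A trace elsewhere is also uncertain. After day 30, section 5.5.1 asks for concomitant medication only in connection with serious adverse events (SAEs) and ECIs, so replacement therapy for a late non-serious endocrine event has no required record under that section.

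What is at stake is the secondary safety endpoint. Section 3.2 hypothesises that adding pembrolizumab is safe without significant toxicity, and any omission of late events moves reported incidence towards that hypothesis. Until 7.1.2.1 is reconciled with 7.2 and 6.1, staff could also record late events differently from one patient to the next.

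**Working it through.** **1. Collection windows side by side**

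| Class of event | Collected until | Section |
|---|---|---|
| All adverse events | 30 days after treatment | 7.2; also 1.0, 5.8, 6.1, 7.1.5.3 |
| All adverse events, general statement | Into follow-up, no end date | 7.1.2.1 |
| SAEs, any cause | 90 days, or 30 days if new anticancer therapy starts | 7.2.3.1 |
| Drug-related SAEs | No end date | 7.2.3.1 |
| The two listed ECIs (overdose without symptoms; combined liver-test criterion) | As for SAEs | 7.2.3.2 |
| Events above Grade 1 already open | Resolution to Grade 0-1 or new therapy | 7.1.5.3 |

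Under the 30-day rule, what remains uncovered is an event with first onset after day 30 that is non-serious and is neither of the two ECIs. Non-serious thyroid, adrenal, skin or lung events fall in that class.

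**2. Visits at which such events could be found** (6.1, 7.1.5.4)

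- Years 1-2: 24 months / 3 = 8 visits.
- Years 3-4: 24 months / 6 = 4 visits.
- Total scheduled: 8 + 4 = 12, none with adverse event review ticked.
- First visit: 3 x 30.44 days = about day 91. This is past day 30 and at or just past the 90-day SAE/ECI window.

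**3. How many of the 12 a patient can reach**

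- Treatment length: 2 + 18 x 3 = 56 weeks, which reproduces the protocol's figure. In months, 56 x 7 / 30.44 = 12.9.
- First patient, 60-month study: 60 - 12.9 = 47.1 months after treatment. Visits at months 3 to 24, 30, 36 and 42 fit, which is 11 of 12.
- Last patient, enrolled at month 24: 60 - 24 - 12.9 = 23.1 months. Visits at months 3 to 21 fit, which is 7 of 12.
- With the permitted gap of up to 4 weeks before pembrolizumab, treatment takes 60 weeks (13.8 months). This leaves 46.2 and 22.2 months, and the counts stay at 11 and 7.

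These counts assume a full course, no recurrence or new anticancer therapy, and closure at month 60. Patients with recurrence or new therapy move to telephone survival contact (7.1.5.5.1) and reach fewer visits.

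**4. Size**

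Reported incidence = patients with at least one qualifying event / 26. If k patients have a late, unrecorded event and no earlier qualifying event, reported incidence falls by k/26:

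- k = 0: no change.
- k = 1: 1/26 = 3.8 percentage points.

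A patient already counted for an earlier qualifying event does not change the figure. The documents give no late-onset rate, so k cannot be derived.

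**The case against.** The best defence is 7.1.2.1. If its reference to follow-up means the whole post-treatment phase, late events are to be recorded. That is a fair reading, and a reader should not infer that the protocol stops at 30 days without contrary text. It does not close the gap, because the same section defers to the flow chart and to 7.2, and both stop at 30 days. If the reference means only the 30-day safety follow-up, the conflict disappears but the gap stands.

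A reader might also infer that late toxicity in general is measured but never counted. The documents do not support that. Drug-related SAEs are reportable at any time, and seriousness includes important medical events and hospitalisation, so some late Grade 3 events would be captured. SAEs and the listed ECIs run to 90 days, and open events above Grade 1 are followed.

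Section 10.6 says that all available data will be displayed and 8.2.2.3 sets no cut-off, so late laboratory values may appear in listings. That stands, but a listed value carries no required grade or causality assessment and does not by itself enter an incidence summary.

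Two further inferences fail. Nothing shows that the loss is greatest in patients who stop early: everyone has the same 30 days after treatment, and no onset-time data are given. Nor do the documents support a total understatement in percentage points, since that needs a count of late events they do not supply.

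Finally, the safety analysis is descriptive, with no threshold or test. This limits the importance of the point but does not remove it.

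**Conclusion.** The point holds in limited form. The 30-day rule in 1.0, 5.8, 6.1, 7.1.5.3 and 7.2 conflicts with 7.1.2.1 as written, and the sections must be reconciled. If the 30-day rule governs, first-onset, non-serious, non-ECI immune-related events found at post-treatment visits need not be recorded, although the protocol expects such events and tests for some of them.

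The effect runs in one direction, towards lower reported toxicity. It is 3.8 percentage points for each affected patient with no earlier qualifying event, assuming all 26 planned patients form the denominator (8.2.3.1 specifies the intent-to-treat population). The number of such patients is unknown and could be zero. Four years of post-treatment testing is the schedule, not the expected exposure: under the stated assumptions, a recurrence-free patient who completes treatment reaches about 7 to 11 of the 12 visits. Only the secondary safety endpoint is affected; the primary endpoint, 1-year RFS, is not. The change is worth making because it is cheap.

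**What to change.** - **6.1:** tick adverse event review at the existing Year-1/2 and Year-3/4 visits, limited to events of possible immunologic etiology.
- **7.2, 7.1.2.1 and 5.5.1:** state the same rule in each, so that these events, and the medication given for them, are recorded after day 30. Sections 1.0, 5.8 and 7.1.5.3 need a matching sentence.
- **8.2.2.3:** state the windows and summarise events up to 30 days separately from late immune-related events. Give the number of patients still attending post-treatment visits beside the late summary, since recurrence or new therapy ends those visits.

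Extending non-serious immune-related events only to the 90-day SAE window would not be enough, because the first post-treatment visit falls at about day 91.

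The cost is protocol and case report form wording, some extra data entry and a slightly higher reported toxicity rate. No new visit or blood test is needed.

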7.2.2 Reporting of Pregnancy and Lactation to the Sponsor and to Merck

Although pregnancy and lactation are not considered adverse events, it is the responsibility of investigators or their designees to report any pregnancy or lactation in a subject (spontaneously reported to them) that occurs during the trial.

Pregnancies and lactations that occur after the consent form is signed but before treatment allocation/randomization must be reported by the investigator if they cause the subject to be excluded from the trial, or are the result of a protocol-specified intervention, including but not limited to washout or discontinuation of usual therapy, diet, placebo treatment or a procedure.

Pregnancies and lactations that occur from the time of treatment allocation/randomization through 120 days following cessation of Sponsor’s product, or 30 days following cessation of treatment if the subject initiates new anticancer therapy, whichever is earlier, must be reported by the investigator. All reported pregnancies must be followed to the completion/termination of the pregnancy. Pregnancy outcomes of spontaneous abortion, missed abortion, benign hydatidiform mole, blighted ovum, fetal death, intrauterine death, miscarriage and stillbirth must be reported as serious events (Important Medical Events). If the pregnancy continues to term, the outcome (health of infant) must also be reported.

Such events must be reported within 24 hours to the Sponsor and within 2 working days to Merck Global Safety. (Attn: Worldwide Product Safety; [contact])

